### **Post-treatment adverse events**

Adverse events with date of onset or worsening after the date of last infusion of study drug + 56 days are considered as post-treatment adverse events.

Based on the extension study database alone, the post-treatment adverse events will not be identified accurately according to above definition. Also, to take into consideration that adverse events starting between Week 25 and Week 29 could potentially fall into the definition of treatment emergent adverse events, adverse events of population II will be summarized by time interval, with adverse events starting date in the interval of:

- Week 25 to Week 25 + 35 days
- Week 25 + 36 days onward

The summary will be done for Population II only.

### **Deaths**

All the deaths in the clinical database will be listed.

Deaths may be summarized by primary reason for death (specification) and will be presented by primary system organ class, PT and treatment group, for each population separately. Contributing reason for deaths will be listed only.

### **Adverse events of special interest (AESI)**

The number (n) and percentage (%) of patients with adverse events of special interest will be summarized by risk level PT (levels 1-7) and treatment group. For each risk level PT, exposure-adjusted incidence rate (IR), will be calculated as the number of patients experiencing at least one AE in each category relative to the total patient years of the “at risk”\*100. The total patients years of the “at risk” is defined, as the the sum of time in years to first occurrence of a particular AE or time in years to EOS visit for subject who did not encounter a particular AE. For Population I, for each treatment group, total exposure will be calculated as the sum of exposure (days) of all patients per treatment group, divided by 365.25 (years). The calculation formula, for the number of days of drug exposure can be found in Section 3.3.1.

### **Other safety evaluations**

#### **Echocardiography**

Summary statistics will be presented by visit and treatment group for the following measurements:

- Left ventricular wall (posterior) and septal thickness
- Left ventricular mass and mass index
- End-diastolic volume
- End systolic volume
- Left ventricular ejection fraction
- Left ventricular diastolic diameter
- Left atrial size and volume
- Right ventricular wall thickness and function
- Interrogation of all valves for function, stenosis, regurgitation and morphology.

Summary statistics for echocardiography measurements at each scheduled visit as relevant, will be presented for each treatment group (see Section 2.1 [Precision and summary statistics]), for each population separately.

Notable echocardiography values are considered to be the following:

- LV posterior wall thickness:
  - change from baseline >50% (increase)
  - wall thickness at the end >15 mm
- Septal thickness:
  - change from baseline >50% (increase)
  - wall thickness at the end >15 mm
- Left ventricular ejection fraction:
  - relative decrease of >15% from baseline
  - absolute value of LVEF <45

For notable echocardiography values, baseline is defined as Week 25.

Summaries of newly occurring notable values will be summarized by population and by epoch, and notable values will be flagged.

All echocardiography results will be listed by Population, treatment, subject and visit/time.

[REDACTED]

[REDACTED]

### **Nutrition status/protein intake**

Nutrition status/protein intake during the study will be similarly as described in 3.2.2.2.1.

#### **3.6.1.3 Graphical presentation of results**

Boxplots to visualize trends in longitudinal safety data (vitals, ECG, lab parameter) will be created.

[REDACTED]

### **3.8 Interim analyses**

An interim analysis will be triggered by the analysis of the core study Part A. Data from primary and key secondary efficacy parameters will be summarized. The interim analysis will provide a preliminary evaluation of endpoints over approximately 12 months; and together with core study Part A data will support next step decision making. Analyses based on PP set will not be included for IA.

The interim analysis will cover following analyses:

- Patient disposition
- Analysis sets
- Demographics and patient characteristics at Week 25 (nutritional status, protein intake, 6MWT, SPPB total score, Gait Speed, [REDACTED], and ASMI)
- Treatments (Study drug for population I, prior and concomitant medication for both populations)

- Primary analysis: SPPB at Week 49, summaries of population I and II separately
- Secondary analyses: 6MWT, Gait speed, LBM and ASMI, summaries for population I and II separately

- █ [REDACTED]
- Safety analyses:
    - Nutrition status/protein intake
    - Population I: TEAE, ECG, Vital sign, and notable Lab
    - Population II: notable Lab.
  - Supportive analysis:
    - Proportion of sarcopenic patients at Week 25 vs Week 49.

█ [REDACTED] Such analysis will be detailed in a separate document when it becomes necessary and/or be generated for the final analysis.

### 3.8.1 Interim Analysis FIR

Among the outputs planned to be released for the IA, key statistical outputs listed below will be released in priority:

- Summary of patients disposition by treatment
- Summary of patients under each analysis set by treatment
- Summary of demographic characteristics by treatment
- Summary of patient characteristics at Week 25 (6MWT, SPPB total score, Gait Speed, █ [REDACTED], and ASMI) by treatment.
- Analysis of primary endpoint: SPPB at Week 49 for both populations.
- In addition to primary endpoint, statistical summary from Week 25 to Week 49 performance along with figures of time course and/or change from Week 25 will be provided for following endpoints (secondary endpoints) for both populations:
  - 6 minute walk test (6MWT)
  - SPPB total score
  - Gait Speed (GS)

### 3.9 Sample size calculation

All the subjects from the core (E2202), if eligible, can enter this extension study after they complete informed consent. The study is not powered for hypothesis testing.

With 40 to 50 patients per each bimagrumab dose arm, assuming a standard deviation of SPPB of 1.5, 2.0, 2.5, and 3.0, the half-width of 95% confidence interval for SPPB is presented below in [Error! Reference source not found.](#)

**Table 3-1: Half-width of 95% confidence interval of SPPB**

	SD=1.5	SD=2.0	SD=2.5	SD=3.0
50 patients per arm	0.42	0.55	0.69	0.83
40 patients per arm	0.46	0.62	0.77	0.93

## 4 Statistical methods planned in the protocol and determination of sample size

Data will be analyzed by Clinbay according to the data analysis section 9 of the study protocol which is available in [Appendix 16.1.1 of the CSR](#). Important information is given in the following sections and details are provided, as applicable, in [Appendix 16.1.9 of the CSR](#).

## 5 Clinical Study Report - Appendix 16.1.9 Documentation of statistical methods

### 5.1 Introduction

This appendix details the statistical methods in addition to the report text. All analyses will be performed by using SAS® Version 9.3 or higher.

### 5.2 Precision and summary statistics

If not otherwise specified, default summary statistics for quantitative variables for all analyses [REDACTED] will include:

- The number of patients in each category (n).
- Mean
- Standard deviation (SD)
- Minimum
- Median
- Maximum

For the Interim Analysis, to avoid patient level unblinding, minimum and maximum will not be included in the summary statistics for all except Safety summaries.

Summary statistics for all qualitative variables will be presented in contingency tables and will include number (n) and percentage (%) of patients. Percentages will be presented to one decimal place. The number of missing assessments will be displayed as part of a “missing” category, where appropriate.

Where Confidence Intervals will be presented alongside the summary statistics, these will originate from a one-sample t-test.

Data will be aligned within tables by the decimal point.

All values will be rounded using the SAS® function ROUND. If the original data has N decimal places (as derived from the raw data) (i.e. decimal precision [N]), then the summary statistics will contain the following decimal places (with a maximum of 3 decimals):

- The minimum, maximum: N.
- The mean and median: N + 1.
- The SD and standard error (SE): N + 2.

For application of inferential statistics, the least squares (LS) means and corresponding confidence intervals (CIs) will be reported with one extra decimal relative to the individual raw data. The odds ratios and corresponding CIs will be reported with two decimal places where relevant.

The p-values will be reported as follows:

- $< 0.0001$  will be presented as “ $<0.0001$ ” (i.e. 0.00009 will be presented as “ $<0.0001$ ”).
- $\geq 0.0001$  will be rounded to four decimal places.

Note: Rounding will be applied after the “ $<0.0001$ ” rule.

All significant p-values (i.e.  $< 0.05$ ) will be flagged by means of an “\*” for ease of review.

### 5.3 Study Day 1 and other study days

The date of first infusion of study drug at the extension study for population I, and the date of the first follow-up visit for population II is defined as Study Day 1. All other study days will be labeled relative to Day 1.

For event dates on or after Day 1, study day for an event date is calculated as: (event date – first infusion/follow-up visit date at extension study) +1, which could be Day 1, Day 2, Day 3, etc.

For event dates before Day 1, study day for an event date is calculated as: (event date – first infusion/follow-up visit date at extension study), which could be Day -1, Day -2, etc., referring to 1 day, 2 days, etc., before Day 1, respectively, subsequently Day 0 is not defined.

## 5.4 Definition of Baseline and post-baseline measurements

Baseline is defined as the core study baseline, for both populations. In the planned analyses, Week 25 has been referred to majority of the time, and it is referring to a relative baseline to the extension study, which is defined as the Visit 1 pre-dose assessments of the extension study (Week 25, EOT visit of the core study) for population I and for population II defined as the Visit 1 assessments of the extension study (Week 25, EOT visit of the core). This visit will be labeled as Week 25 in the reports.

## 5.5 Analysis visits

### 5.5.1 Visit naming

**Table 1** Visit schedule for both populations

Visit No.	Visit	Target Visit Day	Start day of visit window	Mid-point	End day of visit window
1	Week 25	1	-	1	15
2	Week 29	29	16	29	43
3	Week 33	57	44	57	71
4	Week 37	85	72	85	99
5	Week 41	113	100	113	127
6	Week 45	141	128	141	155
7	Week 49 (EOT)*	169	156	169	183
8	Week 53 (EOS)*	197	184	197	End of study

\*For population II, Week 49 (EOS) and no Week 53.

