Between the extension study entry visit (week 25) and the EOS (week 49), newly enrolled patients will only visit the site once for the week 37 visit. In between the visits, the patients will be contacted monthly by phone by the site personnel to enquire on the patient's health status and to check compliance with the  diaries.

For a complete and detailed list of assessments, please refer to [Section 6](#) and [Table 6-1](#).

End of study (EOS)/Week 49

This is the last planned visit in the study. It will take place at week 49 or earlier in case of premature study discontinuation.

Following the EOS visit, the patient will be followed by his/her treating physician according to the local standard of care and the patient's situation.

For a complete and detailed list of assessments, please refer to Section 6 [Table 6-1](#).

[figure not shown]
[figure not shown]

Figure 3-2 Study design for patients enrolled prior to protocol amendment #1

Management of patients enrolled prior to the protocol amendment #1

Patients enrolled prior to the study amendment #1 will continue to be dosed every 4 weeks until week 49 (EOT) and will then have a 4 weeks follow-up period until week 53 (EOS).

These patients will also continue the exercise program described above.

Please refer to [Section 6](#) and the specific [Table 6-2](#) for a complete and detailed list of assessments for these patients.

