5.5.15 Early study termination

The study can be terminated at any time for any reason by Novartis. Should this be necessary, the subject should be seen as soon as possible and treated as a prematurely discontinued subject. The investigator may be informed of additional procedures to be followed in order to ensure that adequate consideration is given to the protection of the subject's interests. The investigator will be responsible for informing IRBs/IECs of the early termination of the trial.

6 Visit schedule and assessments

For patients enrolled after the protocol amendment #1, the full assessment schedule is presented in [Table 6-1](#) below. Patients enrolled prior to the protocol amendment #1 will be followed according to the visit scheduled presented in [Table 6-2](#).

In order to allow sufficient reflection time for the informed consent process, the extension study may be presented and discussed early enough in the core study in order to allow the ICF signature process to be done at the Week 25/core EOT visit. The ICF must not be signed before the core EOT visit to avoid complications in the safety reporting requirements.

Patients following [Table 6-1](#) should be seen for all visits on the designated day within a recommended 'visit window' of +/- 14 days. Day 1 must be the same day as the EOT visit of the core (i.e. the visit date is the date of the EOT visit of the core).

Patients should arrive to the visit fasted when blood samples for laboratory assessments will be taken at that visit.

Assessments for a particular visit may be split over several days. These may not be consecutive days but should respect the visit window period.

Below are some recommendations for organizing and performing the study assessments at visits with blood sampling.

- Assessments should be performed sequentially in the morning as follows: ECG collection, vital signs, blood sampling.
- After blood sampling, patients should be offered breakfast.

For patients enrolled prior to the protocol amendment #1, the visits window to be applied is +/- 3 days. When scheduling the assessments of a visit, the same principle as stated above should apply. In addition, study treatment administration should be the last procedure.

[figure not shown]

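### SAP Table 1 puts Population II on 4-weekly analysis windows that do not fit its three site visits, so a permitted Day 155 final visit is labelled Week 45 and one on Day 184 or later has no label

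*SAP*

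**What the plan says.** SAP Section 5.5.1 has a single window table, titled "Visit schedule for both populations". Columns are target day, start day, mid-point and end day. The rows that matter here are:

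- "Week 45 141 128 141 155"
- "Week 49 (EOT)* 169 156 169 183"
- "Week 53 (EOS)* 197 184 197 End of study"

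The asterisk leads to the only exception for Population II: "For population II, Week 49 (EOS) and no Week 53". No changed start or end day is given for that population.

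The protocol describes a different schedule for Population II. Section 3.1 says that between entry and the end-of-study visit "newly enrolled patients will only visit the site once for the week 37 visit". Table 6-1 shows Weeks 29, 33, 41 and 45 as telephone contacts. Protocol Section 6 says these patients "should be seen for all visits on the designated day within a recommended 'visit window' of +/- 14 days". Population I keeps 4-weekly visits with a window of ±3 days.

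The primary endpoint is SPPB at Week 49 (SAP Section 3.4), analysed on all enrolled patients. SAP Sections 3.4.3 and 5.6 use observed data, with no imputation for a missed visit.

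**The concern.** The windows were built for monthly visits, which only Population I has. Applied to Population II, they can move a real final assessment away from Week 49 in two ways. A visit at the early edge of the recommended window takes the label of a week with no scheduled site visit. A late visit takes the label of a week that the footnote removes for this population.

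Because only observed Week 49 values are summarised, a final SPPB, 6MWT, gait speed or DXA result with the wrong label or none is absent from the Population II Week 49 summary and from the ANCOVA in SAP Section 5.8.2, although it was collected. The plan already expects 30% drop-out (Protocol Section 4), so avoidable loss of collected data is unwelcome. If early or late attendance is related to health, the loss would not be random; the documents give no evidence either way.

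The labelling of late visits would also be left to whoever programs the tables. Protocol Section 5.4 gives the core clinical study team the treatment codes after the interim analysis, so the rule is better fixed in writing.

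**Working it through.** **Inputs.** Target days are 1, 29, 57, 85, 113, 141, 169 and 197 (SAP Table 1). Population II site visits are on Days 1, 85 and 169 (Protocol Table 6-1), with ±14 days (Protocol Section 6). Study Day 1 is the first follow-up visit (SAP Section 5.3), taken to be the Week 25 visit as SAP Section 5.4 and Protocol Section 6 indicate.

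**1. Reproduce the SAP windows.** The SAP does not state its rule, but the limits follow midpoints between neighbouring targets: start = (previous + own)/2 + 1; end = (own + next)/2.

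- Week 37: (57 + 85)/2 + 1 = 72; (85 + 113)/2 = 99.
- Week 45: (113 + 141)/2 + 1 = 128; (141 + 169)/2 = 155.
- Week 49: (141 + 169)/2 + 1 = 156; (169 + 197)/2 = 183.

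All eight rows reproduce exactly. Both Week 49 limits therefore come from neighbours (Weeks 45 and 53) at which Population II has no scheduled site visit.

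**2. Map the permitted days.**

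| Visit | Permitted days | SAP window | Mislabelled permitted days |
|---|---|---|---|
| Week 37, Population II | 85 ± 14 = 71–99 (29 days) | 72–99 | Day 71, to Week 33 |
| Week 49, Population II | 169 ± 14 = 155–183 (29 days) | 156–183 | Day 155, to Week 45 |
| Week 49, Population I | 169 ± 3 = 166–172 (7 days) | 156–183 | none |

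The upper limits agree at Day 183. From Day 184 a Population II visit is outside the recommended window, and the table as written has no row for it.

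**3. Size.** The documents give no distribution of visit days. Assume final visits are normal around Day 169, with a continuity correction. Assume 200 − 45 = 155 Population II patients and the overall 30% drop-out: 155 × 0.7 = 108.5, about 109 completers.

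- P(Day 155) = Φ(−13.5/SD) − Φ(−14.5/SD)
- P(Day ≤ 154) = P(Day ≥ 184) = Φ(−14.5/SD)

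| Assumed SD | Day 155 | Day ≤ 154 | Day ≥ 184 | Total outside 156–183 |
|---|---|---|---|---|
| 5 days | 0.16% (0.2 patients) | 0.19% | 0.19% | 0.5% (about 1) |
| 7 days | 0.77% (0.8) | 1.92% | 1.92% | 4.6% (about 5) |
| 10 days | 1.50% (1.6) | 7.35% | 7.35% | 16% (about 18) |

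Only the Day 155 column concerns visits within the recommended window.

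**4. Check the remedy.** The same midpoint rule on Days 1, 85 and 169 gives:

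- Week 25: up to (1 + 85)/2 = 43.
- Week 37: Day 44 to (85 + 169)/2 = 127.
- Week 49: Day 128 to end of study.

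All 29 permitted days for Week 37, and all 29 for Week 49, then take the right label. At SD 10 the chance of a planned final visit before Day 128 is Φ((127.5 − 169)/10) = Φ(−4.15), about 0.002%.

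**The case against.** The strongest reply is that the mismatch is tiny. The early edge is wrong by one day in 29, and Day 71 does not touch the primary endpoint. There is no formal hypothesis testing, and Population II's primary output is descriptive. All of that stands.

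A reader might infer that final visits permitted by the protocol fall into Week 53. They do not: the permitted range and the Week 49 window both end at Day 183. A reader might also take 1, 5 or 18 patients as the loss among permitted visits. Most of those visits are outside the recommended window; the permitted part is 0.2, 0.8 or 1.6 patients.

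The footnote can also be read more kindly. If Week 49 is Population II's end-of-study visit, it may be meant to take over the open end of the end-of-study row. Late visits would then be kept, and the loss would be the early side only: 0.35%, 2.69% or 8.85%, about 0.4, 2.9 or 9.6 of 109. That reading is possible, but the SAP does not state it, and the printed end day is 183.

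Finally, the intermediate rows do some work. Patients who discontinue have an early end-of-study visit at the site, and those rows keep most such visits out of Week 49. This is a reason not simply to delete the rows without replacing that function.

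What the reply does not remove is that late visits are off schedule, not invalid. The protocol calls the window recommended, visit timing is not among the listed examples of deviations that exclude a patient from the per-protocol set, and the primary analysis uses everyone enrolled.

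**Conclusion.** The point holds in a limited form. As written, Table 1 mislabels one permitted day for the final visit (Day 155) and one for Week 37 (Day 71), and gives no Population II label from Day 184 onward. The certain in-window effect is under 2 of about 109 assumed completers for visit-day SDs of 5 to 10 days. The total, 0.5% to 16%, rests on those assumed SDs, on a normal spread centred at Day 169, on applying the overall drop-out to Population II, and on the literal reading of the footnote. The number of patients actually affected cannot be derived from the documents. The table should be corrected before database lock because it can drop collected primary data and the repair is cheap; it does not show that the Week 49 result would be materially wrong.

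**What to change.** Add a separate Population II window table to SAP Section 5.5.1 for site-visit assessments:

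| Visit | Target day | Window |
|---|---|---|
| Week 25 | 1 | up to Day 43 |
| Week 37 | 85 | Days 44–127 |
| Week 49 (EOS) | 169 | Day 128 to end of study |

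These limits leave no gap. Moving only the Week 37 and Week 49 starts to Days 71 and 155 and deleting the other rows would leave Days 100–154 without a label.

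Give end-of-study visits after premature discontinuation their own label, so that they are listed but not counted as Week 37 or Week 49. This is needed because the wider windows would otherwise absorb them. Where two records fall in one window, the SAP's existing closest-to-target rule can stay.

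The cost is one table and a sentence, with no new data. There are two small downsides. Some early or late scheduled visits will count as Week 49, which a listing of actual visit days would make visible. A discontinuation visit that happens to fall in Days 156–183 counts as Week 49 now and would no longer do so. Table 1 can stay unchanged for Population I.

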### Multiple assessments within visits

For visit multiple records may exist in one particular visit for a particular assessment (e.g. laboratory assessments). The following rules (unless otherwise specified) will be applied to obtain one value per patient per assessment per visit which will be used in the assessment by-visit summaries.

- the closest to the actual target visit day is chosen for both continuous variables and categorical variables based on continuous variables (if two assessments have the same distance, then the earlier one by assessment date or visit date will be chosen);
- For qualitative variables (i.e., laboratory abnormalities or most extreme values analysis), the worst/most extreme (high & low) record will be used.

## 5.6 Handling of missing values/censoring/discontinuations

In general, unless otherwise indicated, no data imputation will be done for the missing values.

## 5.7 Imputation of missing and incomplete dates

Adverse event and concomitant medication dates will be imputed per the Novartis standard tables, listings and figures (TLFs) conventions as detailed in the RAP Module 8 (Programming Specifications). All missing or incomplete dates shall however be listed in by patient data listings as recorded in the eCRF.

